| Return and count IP tablets                                   | -         | -                                  | -               | X               | X               | X                | X                | X                | X                          | X                | -   | -                       |

Abbreviations: BMI = body mass index; CCI [REDACTED]; CXR = Chest Radiograph; DLQI = The Dermatology Life Quality Index; ECG = Electrocardiogram; ET = Early Termination Visit; FCBP = females of childbearing potential; CCI [REDACTED]

CCI IP = Investigational Product; NRS = Numeric Rating Scale; CCI [REDACTED] ScPGA = Scalp Physician Global Assessment; CCI [REDACTED] TB = tuberculosis testing; CCI [REDACTED]

a All baseline assessments must be completed prior to randomization and dispensing of IP.

b Visit 10 will serve as the Early Termination Visit for any subject who prematurely discontinues from the study.

c All subjects who complete the study or discontinue the study early will be asked to enter the Four-week Post-treatment Observational Follow-up Phase.

d Written informed consent will be obtained by the Principal Investigator or designee prior to performing any study assessments.

e CXRs taken within 12 weeks prior to screening will be accepted. CXRs should be performed as indicated by local treatment guidelines or practice for monitoring while on immunosuppressive/immunomodulatory therapy. If such guidelines are not available/applicable, routine CXRs should be performed as per the Table of Events or when clinically indicated.

f The QuantiFERON® Gold test should be used for TB testing in lieu of the tuberculin skin test (TST) or purified protein derivative (PPD) test, if possible.

g FCBP: Serum pregnancy tests will be performed at the Screening and Early Termination/Last Treatment Visit. Urine dipstick pregnancy test(s) will be performed at baseline, prior to dosing. An unscheduled pregnancy test should be administered if the subject has missed a menstrual period. The Investigator will educate all FCBP about the options for and correct use of contraceptive methods at the Screening and Baseline Visits and at any time when a FCBP's contraceptive measures or ability to become pregnant changes.

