### **6.2.1. End of Treatment**

An end of treatment (EOT) evaluation will be performed for subjects who are withdrawn from treatment for any reason as soon as possible after the decision to permanently discontinue treatment has been made. The end of treatment (Visit 10) assessments will also be performed for subjects who complete the study.

During the end of treatment visit, subjects must complete the itch NRS and subject questionnaires prior to any other study procedure being performed. The subject must complete the questionnaires in the following order: 1) body itch NRS, 2) scalp itch NRS, 3) DLQI, CCI  
[REDACTED].

During the end of treatment visit, efficacy assessments may be performed by the investigator or qualified designee at any time during a study visit, but only after the subject has completed the NRS and HRQoL assessments, when required. The investigator performing efficacy assessments shall make independent observations at a given study visit and shall not review previous assessments or subject-derived data in advance of conducting the assessments. When conducting the efficacy assessments, the investigator must complete these assessments in the following order: 1) ScPGA, CCI  
[REDACTED].

The following evaluations will be performed as specified in the Table of Events, [Table 3](#):

- Patient reported outcomes or health-related quality of life (HRQoL)
- Concomitant medications evaluation
- Concomitant procedures evaluation
- Complete physical exam
- Vital signs
- Weight
- Hematology panel
- Chemistry panel
- Urinalysis
- Adverse event evaluation (continuously)
- Efficacy assessments (see [Section 6.4](#))
- Serum pregnancy test
- IP return
- Photography (select sites and involving subjects signing a separate photography ICF)

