The continuous endpoint (ie, change from baseline in DLQI total score at Week 16) will be analyzed based on the ITT population using the analysis of covariance (ANCOVA) model. The ANCOVA model will use the change from baseline as the dependent variable and will include treatment group and stratification factor as independent variables and the baseline value as a covariate variable. Within-group least-squares (LS) mean changes from baseline at Week 16, the associated standard errors (SEs) and 2-sided 95% CIs, treatment differences in LS mean changes from baseline, and the associated 2-sided 95% CIs and p-values, will be derived from the ANCOVA model. Missing values at Week 16 will be imputed using the MI method, with sensitivity analysis using the LOCF method.

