## 11. DISCONTINUATIONS

### 11.1. Treatment Discontinuation

The following events are considered sufficient reasons for discontinuing a subject from the investigational product(s):

- Adverse event
- Lack of efficacy
- Withdrawal by subject
- Death
- Lost to follow-up
- Non-compliance with IP
- Protocol deviation
- Pregnancy
- Physician decision
- Study terminated by Sponsor
- Other (to be specified on the CRF)

The reason for discontinuation of treatment should be recorded in the CRF and in the source documents.

When a subject is discontinued from treatment, the Investigator should make every attempt possible to have the subject evaluated at the Early Termination Visit within 4 days of the last intake of IP.

The decision to discontinue a subject from treatment remains the responsibility of the treating physician, which will not be delayed or refused by the Sponsor. However, prior to discontinuing a subject, the Investigator may contact the Medical Monitor and forward appropriate supporting documents for review and discussion.

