4.2.3. Exploratory Endpoints

CC

- ScPGA: Proportion of subjects with ScPGA score of clear (0) or almost clear (1) with at least a 2-point reduction from baseline by visit
- Itch NRS (Whole Body): Proportion of subjects with ≥ 4 -point reduction (improvement) from baseline in the whole body itch NRS score by visit in apremilast extension phase
- Itch NRS (Scalp): Proportion of subjects with ≥ 4 -point reduction (improvement) from baseline in the scalp itch NRS score by visit in apremilast extension phase

CC
C
I

 - DLQI: Change from baseline in DLQI total score at Weeks 4, 8, 16 and 32

CCI

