The SAS procedure MI will be used to impute missing whole body itch NRS score (or scalp itch NRS score) at the scheduled analysis visits in the Placebo-controlled Phase (Weeks 0 to 16) to create M=25 complete data sets. The missing data patterns will be checked by treatment and stratification factor at Baseline (Week 0), and Weeks 2, 4, 8, 12 and 16. If there are non-monotone missing patterns, two separate imputation procedures will be used to complete the imputation process.

In the first step, the Markov Chain Monte Carlo (MCMC) method will be used to impute missing scores by treatment and stratification factor to create M=25 imputed data sets with monotone missing patterns. The minimum and the maximum values for imputation will be 0 and 10, which correspond to the lowest and the highest whole body itch NRS score (or scalp itch NRS score). The seed will be set to 804529, the imputed values will be rounded to integers and a single chain will be used to produce imputations. In case there are convergence issues, a simple model will be used to impute the missing scores by treatment, with further simplification by dropping both treatment and stratification factor in imputation model if necessary.

In the second step, the predictive mean matching method will be used to impute the remaining missing values for the 25 data sets with monotone missing patterns. The MONOTONE REGPMM statement will be used with seed 447159. The missing values at each visit will be imputed based on treatment, stratification factor, and whole body itch NRS score (or scalp itch

NRS score) at baseline and previous visits. The number of closest observations to be used in the selection will be K=5.

After the completion of imputation, the same CMH method will be used to analyze the 25 complete data sets and the SAS procedure MIANALYZE will be used to combine the results for the statistical inferences.

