In summary, the primary analysis of whole body Itch NRS response (or scalp Itch NRS response) will be performed separately for each post baseline visit in the Placebo-controlled Phase for ITT population using MI method for treating missing values. Supportive analyses will be performed at Week 16 visit for: (1) ITT population treating missing values using the LOCF method, (2) ITT population treating missing values using NRI method. In addition, analyses using CMH test adjusting for the stratification factor at randomization and pooled site will be performed at Week 16 for ITT population using MI method for imputing missing values.

6.4.2. Change from Baseline in Dermatology Life Quality Index (DLQI) Total Score at Week 16

Change from baseline in DLQI total score at Week 16 will be analyzed based on the ITT population using the analysis of covariance (ANCOVA) model. The ANCOVA model will use the change from baseline as the dependent variable and will include treatment group and stratification factor as independent variables and the baseline value as a covariate variable. Within-group least-squares (LS) mean changes from baseline at Week 16, the associated standard errors (SEs) and 2-sided 95% CIs, treatment differences in LS mean changes from baseline, and the associated 2-sided 95% CIs and p-values, will be derived from the ANCOVA model.

The SAS procedure MI will be used to impute missing DLQI total score at the scheduled analysis visits in the Placebo-controlled Phase (Weeks 0 to16) to create M=25 complete data sets. The missing data patterns will be checked by treatment and stratification factor at Baseline (Week 0), and Weeks 4, 8 and 16. If there are non-monotone missing patterns, two separate imputation procedures will be used to complete the imputation process.

In the first step, the Markov Chain Monte Carlo (MCMC) method will be used to impute missing scores by treatment and stratification factor to create M=25 imputed data sets with monotone missing patterns. The minimum and the maximum values for imputation will be 0 and 30, which correspond to the lowest and the highest DLQI total score. The seed will be set to 804529, the imputed values will be rounded to integers and a single chain will be used to produce imputations. In case there are convergence issues, a simple model will be used to impute the missing scores by treatment, with further simplification by dropping both treatment and stratification factor in imputation model if necessary.

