In the second step, the predictive mean matching method will be used to impute the remaining missing values for the 25 data sets with monotone missing patterns. The MONOTONE REGPMM statement will be used with seed 447159. The missing values at each visit will be imputed based on treatment, stratification factor, and DLQI total score at baseline and previous visits. The number of closest observations to be used in the selection will be K=5.

After the completion of imputation, the same ANCOVA model will be used to analyze the 25 complete data sets and the SAS procedure MIANALYZE will be used to combine the results for the statistical inferences.

In summary, the secondary analysis of change from baseline in DLQI total score at Week 16 will be performed for ITT population using MI method for treating missing values. Sensitivity analysis will be performed for ITT population treating missing values using the LOCF method,

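### SAP 6.4.2 leaves Week 12 itch and ScPGA out of the DLQI imputation, which can slightly bias the Week 16 DLQI difference if dropout after Week 12 depends on disease differently by arm

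*Protocol*

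**What the plan says.** Protocol 9.6.1.2 fixes only the method for DLQI: "Missing values at Week 16 will be imputed using the MI method, with sensitivity analysis using the LOCF method". It names no predictors. SAP 6.4.2 does: "The missing values at each visit will be imputed based on treatment, stratification factor, and DLQI total score at baseline and previous visits". The visits in that model are also listed there: "The missing data patterns will be checked by treatment and stratification factor at Baseline (Week 0), and Weeks 4, 8 and 16". This matches the DLQI schedule in SAP 4.2.3 ("Change from baseline in DLQI total score at Weeks 4, 8, 16 and 32"), which has no Week 12.

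Itch and ScPGA are collected at Week 12. The imputations for those endpoints (SAP 6.4.1 and 6.3) check patterns "at Baseline (Week 0), and Weeks 2, 4, 8, 12 and 16".

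Subjects who stop early have a further chance to give a DLQI. Table 3, footnote b, states: "Visit 10 will serve as the Early Termination Visit for any subject who prematurely discontinues from the study". Protocol 6.2.1 gives the questionnaire order at the end-of-treatment visit as "1) body itch NRS, 2) scalp itch NRS, 3) DLQI". Protocol 11.1 asks investigators to try to have the subject "evaluated at the Early Termination Visit within 4 days of the last intake of IP". SAP 5.4 lets discontinuation-visit data enter the analysis windows: Days 71-98 map to Week 12, and Day 99 to the end of the phase maps to Week 16.

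**The concern.** A subject who attends Week 12 and then leaves may have a Week 16 DLQI imputed from a Week 8 DLQI, while newer disease scores go unused. Those scores are relevant. DLQI item 1 (Protocol Appendix F) covers itch, and Protocol 11.1 lists lack of efficacy and adverse events among the reasons for stopping. Week 12 itch and ScPGA could therefore predict both who leaves and what their Week 16 DLQI would have been.

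The planned model is adequate only if, given treatment, stratum and DLQI up to Week 8, leaving after Week 12 is unrelated to Week 12 disease. If that fails unequally in the two arms, the estimated DLQI difference is shifted. One way this could happen is exits for poor efficacy on placebo and for tolerability on apremilast. The documents make that pattern possible but do not establish it.

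**Working it through.** **No plan figure to reproduce.** The documents give no DLQI effect size, SD, power or dropout rate. Every DLQI input below except sample size and allocation is an assumption.

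**Step 1: who is affected.** Take subjects who leave after the Week 12 visit.

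- Early Termination DLQI on Day 99 or later in the phase: it counts as Week 16, so nothing is imputed.
- Early Termination DLQI on Days 71-98: it maps to Week 12, which is not a DLQI visit in the imputation. Its use is not stated, and the latest DLQI in the listed model is Week 8.
- No Early Termination DLQI: the latest DLQI is Week 8.

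If the Week 12 visit is on Day 85 and termination visits are spread evenly over Days 86-112, then 14 of 27 days (52%) fall on Day 99 or later. About half of these leavers are unaffected if all attend the visit, and about a quarter if half attend.

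**Step 2: approximate bias.** Within an arm, let f be the share with Week 16 DLQI imputed in this way. Let b be the DLQI points per SD of the part of the Week 12 score that DLQI history does not explain. Let g be the log-odds of leaving per SD of that part, which is also roughly the gap in means between leavers and stayers. The imputed arm mean is then too low by about f × b × g, so

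bias in (apremilast - placebo) ≈ b × (f_P × g_P - f_A × g_A).

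This is zero when f × g is the same in both arms, and its sign depends on which product is larger.

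Assumed inputs: f = 2% to 8%; g = 0.7; residual SD of Week 16 DLQI given its history = 0.6 × 6.5 = 3.9; correlation r of the Week 12 score with that residual = 0.2 to 0.6. So b = r × 3.9 = 0.78 to 2.34. Example: f = 8%, r = 0.6, dependence on placebo only: 0.08 × 2.34 × 0.7 = 0.131.

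**Step 3: simulation.** Each scenario had 600,000 subjects at 2:1 and a true difference of -3.0. Week 16 DLQI was imputed by regression on arm and DLQI at baseline, Weeks 4 and 8, then analysed by ANCOVA. Positive values are toward no effect.

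| f | r | Formula, placebo only | Simulated, placebo only | Simulated, apremilast only | Simulated, opposite in the arms |
|---|---|---|---|---|---|
| 2% | 0.2 | 0.011 | 0.009 | -0.012 | 0.021 |
| 2% | 0.6 | 0.033 | 0.036 | -0.033 | 0.068 |
| 4% | 0.2 | 0.022 | 0.019 | -0.021 | 0.041 |
| 4% | 0.6 | 0.066 | 0.066 | -0.063 | 0.126 |
| 8% | 0.2 | 0.044 | 0.049 | -0.038 | 0.086 |
| 8% | 0.6 | 0.131 | 0.131 | -0.128 | 0.248 |

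With no dependence, or equal dependence and equal f in both arms, the result was within 0.006 of zero. With the Week 12 score added to the imputation, it was within 0.007 of zero in every scenario. The simulation omits the stratum and uses regression means instead of predictive mean matching draws, so it speaks to bias only.

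**Step 4: heavier loss.** With 5-15% of placebo and 5-8% of apremilast subjects leaving between Weeks 12 and 16, and only placebo exits depending on Week 12 itch (log-odds 1.0-1.5 per SD, about 1.2 DLQI points per NRS point), 1,500 simulated trials per scenario gave 0.06-0.19 points, falling to 0.01-0.02 with Week 12 itch added. These runs credit nobody with a termination DLQI. A further run, also on assumed inputs, gave 0.05-0.21 without a usable termination DLQI and 0.03-0.14 when 25-50% of leavers have one.

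**Step 5: scale.** With SD 6.5 and about 200 v 100 subjects, the unadjusted standard error is 6.5 × √(1/100 + 1/200) = 0.80. A bias of 0.03 to 0.2 points is 0.04 to 0.25 standard errors.

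**The case against.** The strongest reply has four parts.

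- **The Early Termination visit.** A reader might infer that everyone who leaves between Weeks 12 and 16 is imputed from Week 8. The documents do not support that: the visit includes DLQI, and a value on Day 99 or later in the phase is an observed Week 16 score. This stands, and it narrows the point to the other leavers.
- **LOCF.** A reader might also infer that the LOCF analysis simply repeats the Week 8 score. Nothing limits it to scheduled DLQI visits, so a termination DLQI may be what is carried. This stands. What remains is that the SAP does not say whether a value on Days 71-98 qualifies, and that LOCF does not use Week 12 itch or ScPGA either.
- **Bias is conditional.** Leaving out an auxiliary variable does not in itself bias a treatment difference, and the documents give no dropout mechanism. This stands, so no direction can be claimed.
- **Consistency and consequence.** Imputing each outcome from treatment, stratum and its own history is one pre-specified approach across endpoints, and DLQI is last of the 12 tests in SAP 6.2. This stands as a reason for low priority. It does not restore the symmetry it appeals to, because itch and ScPGA have their own Week 12 value in their models and DLQI does not.

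**Conclusion.** The gap is real and minor. For leavers after Week 12 with no DLQI on Day 99 or later in the phase, SAP 6.4.2 ignores Week 12 scores that were collected and that plausibly bear on the missing value. The Week 16 DLQI difference can then be biased if leaving depends on Week 12 disease beyond the DLQI history and does so differently by arm. The plausible size is roughly 0.03 to 0.2 points, with zero when the arms behave alike and 0.25 at the extreme examined.

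It is tempting to conclude that the plan shrinks the apremilast effect. That holds only if the dependence is stronger on placebo; stronger dependence on apremilast reverses the sign. All sizes rest on the assumed dropout, SD and correlations. This is a cheap improvement, not the correction of an error.

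**What to change.** In SAP 6.4.2, before the SAP is finalized ahead of Week 16 unblinding:

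- Add two auxiliary predictors only, Week 12 whole body itch NRS and Week 12 ScPGA, placed before Week 16 DLQI in the monotone REGPMM step. The whole body scale already includes the scalp (Protocol Appendix C). Leave K=5 and the seeds as they are.
- Fill intermittent gaps in these two scores in the MCMC step, with bounds 0-10 and 0-4. Adding them in the second step alone would fail wherever their pattern is not monotone.
- If the MCMC step does not converge, drop these auxiliaries before using the existing fallback of dropping stratum and then treatment.
- State how an Early Termination DLQI on Days 71-98 is used, both in the imputation and in LOCF. It cannot simply become a Week 12 predictor: subjects who stay have no scheduled DLQI at that visit, so its relation to Week 16 DLQI could hardly be estimated.

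The cost is two variables in one PROC MI specification and a sentence or two of text. The downside is a slightly larger imputation model, with some added convergence risk in small treatment-by-stratum cells.

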#### **9.6.1.3. Multiplicity Adjustment**

The primary and secondary efficacy endpoints will be hierarchically ranked for testing in order to control the overall type I error rate in claiming statistical significance at the 2-sided 0.05 significance level. Specifically, for the primary efficacy endpoint (ScPGA response at Week 16), if the 2-sided p-value from the comparison between apremilast 30 mg BID and placebo is below 0.05, the outcome will be considered statistically significant and apremilast 30 mg BID will be declared effective. For any secondary endpoint, statistical significance will be claimed only if its 2-sided p-value is below 0.05 and tests for the primary endpoint and all previous secondary endpoints are significant at the 2-sided 0.05 level. The proposed test sequence for the primary and secondary efficacy endpoints is listed as the following:

- Proportion of subjects with ScPGA score of clear (0) or almost clear (1) with at least a 2-point reduction from baseline at Week 16
- Proportion of subjects with  $\geq 4$  point reduction (improvement) from baseline in the whole body itch NRS score at Week 16
- Proportion of subjects with  $\geq 4$  point reduction (improvement) from baseline in the scalp itch NRS score at Week 16
- Proportion of subjects with  $\geq 4$  point reduction (improvement) from baseline in the whole body itch NRS score at Week 12
- Proportion of subjects with  $\geq 4$  point reduction (improvement) from baseline in the scalp itch NRS score at Week 12
- Proportion of subjects with  $\geq 4$  point reduction (improvement) from baseline in the whole body itch NRS score at Week 8
- Proportion of subjects with  $\geq 4$  point reduction (improvement) from baseline in the scalp itch NRS score at Week 8
- Proportion of subjects with  $\geq 4$  point reduction (improvement) from baseline in the whole body itch NRS score at Week 4
- Proportion of subjects with  $\geq 4$  point reduction (improvement) from baseline in the scalp itch NRS score at Week 4

- Proportion of subjects with  $\geq 4$  point reduction (improvement) from baseline in the whole body itch NRS score at Week 2
- Proportion of subjects with  $\geq 4$  point reduction (improvement) from baseline in the scalp itch NRS score at Week 2
- Change from baseline in Dermatology Life Quality Index total score at Week 16

#### **9.6.1.4. Exploratory Endpoints**

Descriptive summary statistics or proportion of subjects achieving specified criteria will be summarized by treatment group. When appropriate, exploratory endpoints at Week 16 will also be analyzed using CMH or ANCOVA methods similar to the primary and secondary endpoints.

#### **9.6.1.5. Subgroup Analysis**

Subgroup analyses for ScPGA response at Week 16 and proportions of subjects with  $\geq 4$ -point reduction (improvement) from baseline in the whole body itch NRS or scalp itch NRS scores at post baseline time points based upon baseline demographic (age, gender, race, etc.) or baseline disease characteristics will be provided to determine the robustness of the treatment effect.

CC1 [REDACTED]  
[REDACTED]  
[REDACTED]

